## Influence of aging on the perioperative dosage of methadone

### Introduction

Increasingly, elderly patients undergo anesthesia and surgery. There are multiple factors that affect the dosage of anesthetic drugs in this age group, such as the normal aging process, age-related morbidity and polypharmacy, commonly observed in the elderly patient (1). The older adult presents pharmacodynamic and pharmacokinetic changes associated with alterations in absorption, distribution, metabolism, and excretion, which commonly translate into an increase in the potency of the drugs, so significant dose reductions may be required(1-5).

Opioids are non-steroidal analgesic drugs widely used in the management of intra and postoperative pain. Numerous studies have described important changes in the pharmacokinetics and pharmacodynamics of these drugs in the elderly population (3,6,7). Morphine clearance, for example, is reduced by 50% in the elderly compared to the young adult, which may prolong the action of this drug in the first group (6). The potency of fentanyl or remifentanil increases progressively with age, requiring substantially lower concentrations in the elderly compared to a young adult to obtain the same effect (3,8).

Methadone is considered a first-line opioid in the treatment of chronic pain due to numerous advantages compared to other opioids (9). Methadone does not generate active metabolites after its liver biotransformation (10), it has a long half-life that translates into a prolonged effect and simple dosing schedules (10), it has antihyperalgesic and antiallodynic properties that give it great effectiveness in the relief of neuropathic pain (11). Despite these advantages, the use of methadone in the surgical population is comparatively less than other opioids such as morphine or fentanyl. Although the general recommendation for the use of opioids in the elderly is to decrease the doses, the great inter-individual variability characteristic of elderly patients and the greater susceptibility to adverse effects in this population, make anesthetic dosing challenging and requires a new approach, to establish more precise dosages in terms of effectiveness and safety. However, to date there are no pharmacokinetic or pharmacodynamic studies that allow standardizing a dose adjustment of methadone in the elderly patient.

### Research Question:

What is the influence of age, on intraoperative methadone dosing, in adult patients undergoing laparoscopic abdominal surgery under general anesthesia?

### General objective:

Generate a population pharmacokinetic and pharmacodynamic model, that allows the generation of reference dosage schedules for intraoperative use of methadone, according to the age of the patient.

### Specific objectives:

- 1) Characterize the changes in methadone volumes and clearance, attributable to age in the adult population.
- 2) Characterize the changes in methadone potency, attributable to age in the adult population.
- 3) Design intraoperative methadone dosing schedules, according to the age of the patient.

### Materials & Methods

This study is a controlled, randomized, double-blind study.

- Inclusion criteria: Age> 18 years, ASA I, II or III, Laparoscopic Abdominal Surgery
- Exclusion Criteria: BMI> 35, opioid use up to 5 days prior to surgery, acute liver failure or chronic liver disease Child C, kidney insufficiency with creatinine clearance estimated by Cockcroft-Gault formula <60 ml / min.

### Recruitment

Recruitment will be carried out by the Research team of the Anesthesiology Division, by daily review of the surgical table and the application of inclusion and exclusion criteria. On the day of hospital admission, patients will be explained what the study consists of and they will proceed to sign the informed consent if they agree to participate in it.

### **Distribution by random groups**

Patients who agree to participate will be randomized into four groups according to the dose of intravenous methadone to be received during anesthetic induction. Group P (placebo), Group M1 (0.05 mg / kg), Group M2 (0.1 mg / kg), and Group M3 (0.2 mg / kg). The random sequence will be generated on a research laboratory computer and will be stored in an encrypted file. This information will be known exclusively by a member of the research team present during the surgery, who will hand over preparing the corresponding medicine in a 20 cc syringe and hand it over to the treating anesthesiologist.

### **Anesthesia**

General anesthesia will be administered in a standard way including frontal electroencephalogram with BIS. The only opioids that patients will receive will be remifentanil and methadone in doses defined according to the corresponding group. Methadone will be administered once the patient is intubated and has hemodynamic stability.

### **Postoperative**

Upon admission to the recovery unit, the patient is given a PCA pump for intravenous administration of morphine. In the first two hours after admission to the recovery unit, the patient will be evaluated every 30 minutes and subsequently these evaluations will be carried out just before taking the blood samples for measurement of plasma methadone. Patient evaluations will be compiled by the research assistant in charge who will be blind to the methadone doses administered.

### **Blood Sampling**

Five venous blood samples will be taken from each patient, for plasma methadone analysis. Patients will be randomly divided into two groups of sampling times: Group 1 at 0.05, 0.75, 1.5, 6, 18 hours after drug administration and Group 2 at 0.25, 1, 3, 12 and 24 hours. Blood samples will be collected in heparin tubes and centrifuged at the UC-Christus Health Network Central Laboratory to be plasma separated and labeled. The extracted serum will be placed in cryo tubes that will be stored at 20 ° C until analysis. Methadone samples will be analyzed using a high performance liquid chromatography (HPLC) spectrofluorometric method at the UC Faculty of Chemistry. The lower limits of quantification (LLOQ) will be determined. Those responsible for the sample collection process, and the coordination for the centrifugation process and transportation to the San Joaquín Campus will be the research nurse and the research fellow.

Once obtained, the blood samples will be sent to the Central Laboratory of the UC-Christus Health Network to be separated in plasma and then they will be sent to the laboratory of the Faculty of Chemistry in San Joaquín, where they will be processed for the specified measurements. Later they will be eliminated according to the corresponding protocol of the laboratory.

### **Data collection**

The data obtained will be collected in a form within the REDCAP computer system, to subsequently generate an encrypted database, maintaining the confidentiality of the recruited patients. The study will be prospectively registered at [clinicaltrials.gov](https://clinicaltrials.gov).

### **Pharmacokinetic analysis**

One, two and three compartment linear models will be used to fit the methadone plasma concentration data over time. Models will be parameterized in terms of elimination clearance, inter-compartment distribution clearance, central volume, and peripheral distribution volumes, as appropriate. Estimates of population parameters (clearance and volumes) will be obtained using nonlinear mixed effects models (NONMEM VII, Icon Development Solutions, [name], USA).

### **Pharmacodynamic analysis**

The use of rescue morphine in the PACU will be used as a measure to relate the methadone dose (mg / kg) with the analgesic efficacy using an EMAX model. The data will be modeled using NONMEM VII. A proportional term will be used for variability between subjects. Additive and proportional terms will be used to characterize the unknown residual variability. The convergence criterion will be three significant digits.

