### **Pharmacodynamic analysis**

The use of rescue morphine in the PACU will be used as a measure to relate the methadone dose (mg / kg) with the analgesic efficacy using an EMAX model.

$$Morphine\ Rescue\ Dose\ (mg/kg) = SO \times \frac{Dose\ (mg/kg) \times Emax}{Dose\ (mg/kg) \times ED50}$$

$SO$  is the required morphine rescue without the use of methadone, EMAX is the maximum required morphine rescue dose and ED50 is the methadone dose that reaches half of this maximum morphine rescue dose. The data was modeled using NONMEM VII. A proportional term was used for variability between subjects. Additive and proportional terms were used to characterize the unknown residual variability. The convergence criterion was three significant digits.

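### Rescue morphine in the PACU is the only efficacy response, so the efficacy model cannot show how long a single dose works or whether that varies with age

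*Combined protocol and SAP*

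**What the plan says.** The two sections headed Pharmacodynamic analysis name one efficacy response, rescue morphine in the PACU: "The use of rescue morphine in the PACU will be used as a measure to relate the methadone dose (mg / kg) with the analgesic efficacy". The model is an Emax function of dose in mg/kg, and its potency parameter is defined on the dose scale: "ED50 is the methadone dose that reaches half of this maximum morphine rescue dose". It contains no written term for time, methadone concentration or age. The section Analysis of covariables specifies scaling by body weight only.

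Four other parts of the plan bear on this:

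- **Introduction.** Among methadone's advantages, "it has a long half-life that translates into a prolonged effect and simple dosing schedules".
- **Anesthesia.** There is a single intraoperative dose: "Methadone will be administered once the patient is intubated and has hemodynamic stability".
- **Postoperative.** Morphine PCA begins on arrival in recovery: "Upon admission to the recovery unit, the patient is given a PCA pump for intravenous administration of morphine". Evaluations are half-hourly for two hours, and "subsequently these evaluations will be carried out just before taking the blood samples for measurement of plasma methadone". The plan does not say what is recorded, when PCA ends or how long patients stay in the PACU.
- **Blood Sampling.** The sampling times differ between two randomized groups: "Group 1 at 0.05, 0.75, 1.5, 6, 18 hours after drug administration and Group 2 at 0.25, 1, 3, 12 and 24 hours".

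The schedules are to come from a combined pharmacokinetic and pharmacodynamic model (General objective). The sample size targets a 20% fall in elimination clearance (Sample size).

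**The concern.** Patients of two ages could need the same morphine in early recovery while the effect of their dose lasts for different times. The planned efficacy data would not tell them apart. Age-related schedules built on those data would reflect early recovery only, although a lasting effect is one of the properties for which the drug is recommended.

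Clearance is the quantity that the trial is sized to study, and it acts mainly on later concentrations. The plan writes no step that carries estimated clearance into the efficacy model, because that model takes dose as its input. Follow-up that could address duration is already scheduled, but no analysis uses it.

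**Working it through.** **The plan's own figure.** The requirement of about 50 patients for a 20% clearance fall at 80% power cannot be reproduced. Between-subject variability, alpha and sidedness are not given. A stand-in two-group comparison of log clearance (difference ln(1/0.8) = 0.223, equal groups, alpha 0.05) returns 50 only if the coefficient of variation is about 29% (two-sided) or 33% (one-sided). The figure is neither confirmed nor refuted, and nothing below depends on it.

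**Inputs.**

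- Clearance fall of 20%, from Sample size.
- End of the later window at 24 h, the last time in Blood Sampling.
- Half-life of 12, 24 or 48 h: assumed, since the documents give none.
- PACU time of 3-5 h after the dose: assumed, since the lengths of surgery and PACU stay are not given.
- One compartment, volume unchanged: a simplification.

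**Formulas.** Let k = ln 2 / half-life.

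- Concentration ratio at time t, reduced against reference clearance: exp(0.2 k t).
- Exposure ratio from a to b: {[exp(-0.8ka) - exp(-0.8kb)] / 0.8} / [exp(-ka) - exp(-kb)].

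**Worked case, half-life 24 h** (k = 0.02888 per h):

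- At 4 h: exp(0.2 × 0.02888 × 4) = 1.023, a rise of 2.3%.
- From 4 to 24 h: [(0.9117 - 0.5743) / 0.8] / (0.8909 - 0.5000) = 0.4217 / 0.3909 = 1.079, a rise of 7.9%.
- From 18 to 24 h: [(0.6598 - 0.5743) / 0.8] / (0.5946 - 0.5000) = 0.1068 / 0.0946 = 1.128, a rise of 12.8%.

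**Range.** Percentage rise caused by a 20% fall in clearance:

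| Half-life (assumed) | Concentration at 3 / 4 / 5 h | Exposure from 3 / 4 / 5 h to 24 h | Exposure 18-24 h |
|---|---|---|---|
| 12 h | 3.5 / 4.7 / 5.9 | 14.4 / 15.3 / 16.2 | 27.2 |
| 24 h | 1.7 / 2.3 / 2.9 | 7.5 / 7.9 / 8.2 | 12.8 |
| 48 h | 0.9 / 1.2 / 1.5 | 3.8 / 4.0 / 4.2 | 6.2 |

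Dividing the second column of results by the first, before rounding, gives 2.7 to 4.4. The window to 24 h is therefore roughly 3-4 times as sensitive to the clearance change as the PACU time.

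**Later evaluations as scheduled.** After the first two hours their times follow the sampling group: 6 and 18 h in Group 1; 12 and 24 h in Group 2, plus 3 h if that time has not already passed. Group 1 has no scheduled 24 h evaluation.

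**The case against.** **Clearance is measured elsewhere.** A reader might infer that an age-related fall in clearance cannot show in the data behind the schedules. The documents do not support that. Plasma is sampled to 18 or 24 h, clearance is estimated from it, and the sample size is aimed at it. The gap is confined to the efficacy data.

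**Duration is not a stated objective.** This is correct. The specific objectives name volumes and clearance, potency, and schedules. The remark on prolonged effect sits in a list supporting methadone for chronic pain. Early morphine need is a defensible response for potency. What stands is narrower: the efficacy model cannot support a statement about duration.

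**The size can be overstated.** Comparing the single 24 h concentration with that at 3-5 h gives a ratio of about 5 to 9. A cumulative morphine total includes the early hours, so 3-4 is the relevant figure. Nor is it shown that a rise of about 8% in exposure would be visible in morphine use with 20 patients per age band, or about 20 / 4 = 5 per band and dose group if allocation is equal (assumed).

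**A longer window alone is not enough.** This also stands. A second response in the same dose-driven model would still not bring clearance or age into efficacy.

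**Unequal times can be modelled.** Mixed-effects models accept them, so the staggered evaluations are not a flaw in themselves. Common times are still useful, because a morphine total to 24 h needs a 24 h reading in both groups.

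**Conclusion.** The point holds for the efficacy data. With PACU rescue morphine fitted to administered dose as the sole efficacy response, the trial cannot describe how long the analgesic effect of one dose lasts or whether this depends on age. Under the stated assumptions, a 20% fall in clearance changes concentration by about 1-6% in the PACU, by about 4-16% as exposure from then to 24 h, and by about 6-27% as exposure over 18-24 h.

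The half-lives, the PACU time and the one-compartment form are all assumed, and the figures do not translate directly into morphine use. The contrast between early and late windows persists across the ranges shown; its exact size does not. This is an inexpensive improvement to a plan whose pharmacokinetic part is unaffected. It is best made before recruitment, since pump totals not recorded at the time may not be recoverable.

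**What to change.** 1. Keep rescue morphine in the PACU as the early response.
2. Record PCA pump totals at the same times for every patient, whatever the sampling group (for example 6, 12, 18 and 24 h after methadone), for as long as PCA is in use under planned care. Treat readings after PCA stops or after discharge as incomplete.
3. Analyse interval and cumulative morphine to 24 h as a second response, linked to model-predicted methadone concentration over time, with age as a covariate. This link is what lets estimated clearance reach efficacy.
4. Limit any statement about duration in the schedules to what this analysis supports.

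The cost is a few extra pump readings and one more model fit, with late data possibly incomplete. Dosing, analgesic care, patient numbers and blood draws do not change.

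### With one PACU rescue amount per patient, the planned proportional between-subject and proportional residual terms cannot be separated (term on S0) or not usefully so (term on Emax or ED50)

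*Combined protocol and SAP*

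**What the plan says.** The plan has two sections headed Pharmacodynamic analysis, one after Pharmacokinetic analysis and one after Analysis of covariables. Both take PACU rescue morphine as the response: "The use of rescue morphine in the PACU will be used as a measure to relate the methadone dose (mg / kg) with the analgesic efficacy", through an Emax model. The first section specifies the variance model: "A proportional term will be used for variability between subjects", and "Additive and proportional terms will be used to characterize the unknown residual variability". The second repeats it in the past tense ("Additive and proportional terms were used to characterize the unknown residual variability") and prints an equation with one morphine rescue dose in mg/kg on the left and no time index. In it, S0 "is the required morphine rescue without the use of methadone" and multiplies the whole prediction.

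Under Distribution by random groups, patients are "randomized into four groups according to the dose of intravenous methadone to be received during anesthetic induction": placebo, 0.05, 0.1 or 0.2 mg/kg. Each patient therefore contributes one dose level.

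Under Postoperative, the patient has a morphine PCA pump and, for the first two hours in recovery, "the patient will be evaluated every 30 minutes". Neither pharmacodynamic section says whether interval amounts enter the model, and neither names the parameter that carries the between-subject term. Model fit quality plans 1000 bootstrap repetitions for the parameter confidence intervals.

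**The concern.** A between-subject variance can be told apart from a residual variance in two ways: by repeated records within a patient, or by a different dependence on the predicted value. A static model with one amount per patient lacks the first. If both terms are proportional to the same prediction, it lacks the second as well.

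At stake is a reported output of the population model, the between-patient variance of the analgesic response, together with its bootstrap interval. If the data do not determine the split, the value printed depends on starting values and the optimiser. Bootstrapping does not repair that, and a convergence criterion of three significant digits means little for components lying on a flat ridge of the likelihood.

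**Working it through.** **Plan's own figure.** There is none to reproduce. The sample-size section (about 50 patients, 80% power, 20% fall in clearance) concerns pharmacokinetics only. No pharmacodynamic variance or sample size is given.

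**Inputs from the plan.** Four doses (0, 0.05, 0.1, 0.2 mg/kg); 60 patients; one methadone dose each; the variance terms above.

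**Assumptions, not in the plan.** Fifteen patients per dose (the allocation ratio is not stated). Curve f(D) = S0 × (1 − Emax × D/(ED50 + D)), with S0 = 0.15 mg/kg, Emax = 0.8, ED50 = 0.06 mg/kg. Between-subject variance w² = 0.16 (CV 40%), proportional residual variance s² = 0.09 (CV 30%), additive SD 0.02, so a² = 0.0004. All results use the first-order normal approximation.

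**Why a curve must be assumed.** As printed, the fraction is (Dose × Emax)/(Dose × ED50). The dose cancels, leaving S0 × Emax/ED50, which is constant over dose. Under that form the variance block has rank 1 of 3, with the term on S0 or on ED50.

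**One record per patient, term on S0.** S0 scales the whole prediction, so

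Var(y) = f(D)² × w² + f(D)² × s² + a² = f(D)² × (w² + s²) + a².

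The derivatives with respect to w² and s² are both f(D)² at every dose. The rank is 2 of 3 and the information matrix is singular. This holds whatever parameter values are assumed. In one simulated data set of 60 patients:

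| w² fixed at | CV | fitted s² | sum | −2LL |
|---|---|---|---|---|
| 0.0001 | 1% | 0.0783 | 0.0784 | −324.5005 |
| 0.02 | 14% | 0.0584 | 0.0784 | −324.5005 |
| 0.04 | 20% | 0.0384 | 0.0784 | −324.5005 |

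The likelihood is flat until w² uses up the whole sum, that is, up to a CV of √0.0784 = 28%. The sum is itself loosely estimated: at w² = 0.16, with s² = 0, −2LL rises only to −323.7044. The flat ridge is the point here, not the level.

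**One record per patient, term elsewhere.** The between-subject part is now (∂f/∂ln θ)² × w², zero on placebo and varying with dose, so the rank is 3 of 3. Relative to f(D)², its multiplier for ED50 is 0, 0.097, 0.141 and 0.136 at the four doses, so it adds little to the variance. For Emax it is 0, 0.33, 1.00 and 2.56. Relative standard errors (RSE):
- Emax: 184% for w², 144% for s², correlation 0.90.
- ED50: 579% for w², 55% for s².

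**One combined proportional variance.** With w² + s² = 0.25 as a single parameter plus a², the rank is 2 of 2 and the combined variance has an RSE of 49%. The additive variance stays weakly determined (185%).

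**Four interval records per patient**, treated as independent given the patient, with the same values:
- Term on S0 only: rank 3 of 3; RSE 25% for w² and 36% for s².
- Terms on both S0 and ED50 (each 0.16): rank 4 of 4, but the RSE of the ED50 variance is 451%.

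**The case against.** The strongest reply is that the plan never says one total per patient. The Postoperative section has a PCA pump and says "the patient will be evaluated every 30 minutes and subsequently these evaluations will be carried out just before taking the blood samples", so repeated records are possible. This stands: one amount per patient is an inference from a static equation in dose, and the result is conditional on it. It is still the natural reading, because nothing in either pharmacodynamic section brings interval amounts or time into the model.

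Second, the parameter carrying the between-subject term is not named, and on Emax or ED50 the components are formally separable. This stands for the algebra. It does not rescue the estimate, given RSEs of 184% and 579%, though those figures depend on the assumed values.

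Third, a reader might infer that the age-specific dosing schedules rest on this between-patient spread and are therefore arbitrary too. The documents do not support that. The objectives ask for schedules by age and do not mention between-patient spread. Schedules built on typical values would use S0, Emax, ED50 and the age effects. With the term on S0, the sum of the two variances still fixes the total spread of observed rescue.

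Fourth, a reader might take the proportional term to imply negative values of S0 or ED50. The plan gives no formula for the term, and to first order proportional and exponential coding coincide, so this adds nothing.

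**Conclusion.** The concern holds conditionally. If one rescue amount per patient is modelled, the stated variance model leaves the between-patient variance unidentified with the term on S0 (rank 2 of 3, independent of assumed values, to first order). With the term on Emax or ED50 it is practically uninformative (RSE about 180% and 580%, under the assumed values and 15 patients per dose). Under a log-normal between-subject term, only the shape of the distribution could tell the components apart.

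The damage is confined to the reported split and its bootstrap interval. It would be going too far to call the two components inseparable in every case. This should be corrected, but it does not invalidate the pharmacodynamic objective. The printed equation needs correcting before any version of the model can be fitted.

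**What to change.** In both Pharmacodynamic analysis sections, after correcting the equation, state the records that enter the model and the parameter that carries the between-subject term. Then choose one option:

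- **One total per patient.** Keep a single proportional component (drop either the proportional residual or the between-subject term) plus the additive term, and report it as combined between-patient and residual variance. This costs only wording. The downside is that no separate between-patient variance is reported.
- **Separate components.** Do this only if PCA amounts by interval, for example the 30-minute evaluations over the first two hours, are recorded and modelled as repeated measures within patient. Use a single between-subject term, for example on S0, because a second one on ED50 stays practically undetermined (about 450% RSE). This costs data capture that the plan does not now describe, and a model for demand over time, with zeros and serial dependence. The RSEs of 25% and 36% above ignore such dependence and are therefore optimistic.

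The choice should be made before data collection, since interval amounts have to be captured as they occur.
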